Title	A prospective, post-market, multi-center study of the outcomes of the Rejuvenate® Modular Hip System
Short Title	Rejuvenate® Modular Outcomes Study
Protocol Number	68
Phase	Post-market
Methodology	
This study will be a prospective, non-randomized evaluation of the Rejuvenate® Modular Hip System for primary total hip replacement (THR) with a cementless application in a consecutive series of patients who meet the eligibility criteria.
 
Data from Secur-Fit™ HA monolithic femoral stem cases that are enrolled in the Trident® X3® Polyethylene Insert Study will be used as a historical control group.

Study Duration	
• Minimum functional evaluation, assessment of health related quality of life (QOL) and radiographic follow-up of each primary THR case to 5 years• Enrollment period of 24 months• Completion of pain, satisfaction and survivorship patient questionnaire between 6 and 10 years• Approximate 12-year total duration
Study Center(s)	10 – 12
Hypothesis	The success rate, defined as freedom from femoral stem/neck construct revision/removal for any reason, for hips implanted with the Rejuvenate® Modular Hip System, is no worse than for hips implanted with the Secur-Fit™ HA monolithic femoral hip stem at 5 years postoperative.

CONFIDENTIAL

Objectives	
Primary:
 
• To evaluate the success rate of cementless primary THR with the Rejuvenate® Modular Hip System as compared to the Secur-Fit™ HA monolithic femoral hip stem, through absence of revision at 5 years postoperative. 
Secondary:
 
• To obtain natural preoperative biomechanical measurements and compare a preoperative plan to postoperative biomechanical measurements, within the Rejuvenate® Modular Hip System group.• To compare pain, function and health related QOL between the Rejuvenate® Modular Hip System group and the Secur-Fit™ HA monolithic femoral stem group. The following outcomes measures will be used for this comparison:
○ Harris Hip Score (HHS)○ Short Form-12 (SF-12)○ Lower Extremity Activity Scale (LEAS)• To review radiographic stability and complications between those implanted with the Rejuvenate® Modular Hip System and the Secur-Fit™ HA monolithic femoral stem group. Published complication rates with similar devices as well as complications related to modularity will be reviewed, as applicable.
Number of Subjects	240 cases

CONFIDENTIAL

	
Inclusions:
 
A. Patient has signed an IRB approved, study specific Informed Patient Consent Form.B. Patient is a male or non-pregnant female age 18 years or older at time of study device implantation.C. Patient has primary diagnosis of Non-Inflammatory Degenerative Joint Disease (NIDJD).D. Patient is a candidate for a primary cementless total hip replacement.E. Patient is willing and able to comply with postoperative scheduled clinical and radiographic evaluations and rehabilitation.F. Patient's operative femur templates to Rejuvenate® Modular Stem size 7-12. 
Exclusions:
 
G. Patient has a Body Mass Index (BMI) ≥ 40.H. Patient has an active or suspected latent infection in or about the affected hip joint at time of study device implantation.I. Patient has a neuromuscular or neurosensory deficiency, which limits the ability to evaluate the safety and efficacy of the device.J. Patient is diagnosed with a systemic disease (e.g. Lupus Erythematosus) or a metabolic disorder (e.g. Paget's Disease) leading to progressive bone deterioration.K. Patient is immunologically suppressed or receiving steroids in excess of normal physiological requirements (e.g. > 30 days).L. Patient requires revision surgery of a previously implanted total hip replacement or hip fusion to the affected joint.M. Patient has a known sensitivity to device materials.N. Patient is a prisoner.
--	--

CONFIDENTIAL

Study Device	
Rejuvenate® Modular Hip System
 
Required Components:
 
• Rejuvenate® Modular Stem• Rejuvenate® Modular Neck 
The femoral components must be used in a cementless application.

Reference Therapy	Secur-Fit™ HA Monolithic Femoral Hip Stem
Ancillary Devices	
Stryker acetabular components and femoral bearing heads must be used according to this study protocol. The following ancillary devices are permissible:
 
• Stryker Trident® or Titanium™ Primary acetabular shells, with or without screw fixation, as well as Stryker Restoration® ADM acetabular shells• Stryker alumina ceramic inserts (for use with Trident® acetabular shells) or X3® inserts• Stryker LFIT™ CoCr heads; delta ceramic heads; or alumina ceramic heads with adaptor sleeve

CONFIDENTIAL

Statistical Methodology	
Primary:
 
The 90% confidence interval around the difference in success rate (Rejuvenate® Modular Hip System – Secur-Fit™ HA monolithic femoral stem) will be computed at 5 years postoperative. For the non-inferiority comparison, the lower bound of this 90% confidence interval will be compared with -5%.
 
Secondary:
 
• A t-test or Wilcoxon test will be used to compare the postoperative biomechanical measurements to a preoperative plan.• Independent group t-tests will also compare HHS, SF-12 and LEAS at applicable time points between the Rejuvenate® Modular Hip System and Secur-Fit™ HA monolithic femoral stem groups. In addition, a paired t-test will compare the results preoperatively with each postoperative evaluation within the Rejuvenate® Modular Hip System group.• The adverse event (AE) rates and 95% confidence intervals will be presented within the Rejuvenate® Modular Hip System group. A Fisher's exact test will be used to compare the AE rates between the Rejuvenate® Modular Hip System and the Secur-Fit™ HA groups, if appropriate.• Radiographic data will be summarized in table format.
--------------------------------	---

CONFIDENTIAL

Evaluation Schedule

Evaluation	Preop X-rays (-1 yr) CRFs (-4 mos)	Intraop	6 weeks (± 3 wks)	1 year (± 2 mos)	2 years (± 2 mos)	3 years (± 3 mos)	4 years (± 4 mos)	5 years (± 4 mos)	6 years (± 4 mos)	7 years (± 4 mos)	8 years (± 4 mos)	9 years (± 4 mos)	10 years (± 4 mos)
Inclusion/ Exclusion	X												
Demographics & Medical History	X												
Preoperative Functional Evaluation	X												
Preoperative Biomechanical Measurements	X												
Surgical Details		X											
Postoperative Functional Evaluation			X	X	X	X	X	X		Optional			Optional
Postoperative Biomechanical Measurements			X										
SF-12	X		X	X	X	X	X	X		Optional			Optional
LEAS	X		X	X	X	X	X	X		Optional			Optional
Radiographs: Anteroposterior (AP) pelvis, AP femur, lateral	X		X	X	X	X	X	X		Optional			Optional
Follow-up Questionnaire									X	X	X	X	X

Functional Evaluation: The Functional Evaluations include the HHS, a subjective outcomes tool completed by the investigator that measures function, pain and motion.

SF-12: The SF-12 is a 12 item patient questionnaire that evaluates general health and well being.

LEAS: The LEAS is a self-administered patient evaluation designed to reflect patient activity.

Follow-up Questionnaire: The Follow-up Questionnaire is a short patient questionnaire intended to provide information on patient satisfaction, pain and whether or not there have been any revisions or removals of the study device since the last follow-up visit.

CONFIDENTIAL

1 Introduction

This document is a protocol for a human research study. This study will be conducted in compliance with the protocol, Good Clinical Practice (GCP) Standards, associated Federal regulations and all applicable research requirements.

1.1 Background

Modular hip prostheses have been in clinical use since 1985. In a study of 216 anatomic cementless THRs (208 patients) with ceramic bearings and modular necks, followed for a minimum of 3 years, the authors affirm that the advantages of this method include its adaptability to a variety of anatomical conditions. From a clinical standpoint, all of the patients achieving long-term follow-up demonstrated improvement in pain, movement and walking. Radiographically, bone stability was observed in 98.8% of stems. A total of 99.4% of stems were osseointegrated and only one case showed osteolysis requiring revision of stem and cup after 2 years. This data supports the conclusion that neck modularity has not changed the survivorship of standard primary hip femoral components, while facilitating implantation in patients with varied anatomical conditions.¹

A review by Spitzer² of a similar modular device's 20-year clinical history shows that the prosthesis has performed well in both primary and revision cases. The modular junction has survived with long-term clinical follow-up. The author argues that despite concerns regarding fretting and failure at the modular junction, mid to long-term follow-up indicates that these issues do not pose a significant concern. Furthermore, fixation by the proximal sleeve has proven reliable and durable, and loosening rates have been low, as evidenced by clinical data.³

Stryker is introducing a modular hip prosthesis, the Rejuvenate® Modular Hip System. The basic design of the Rejuvenate® Modular Hip System is similar to other total hip systems, both modular and monolithic, which are currently commercially distributed. The Rejuvenate® Modular Hip System's design features are based upon the previous success of Stryker's hydroxylapatite (HA) coated monolithic femoral components.

CONFIDENTIAL

Table 1. Rejuvenate® Modular Hip System Design Features

Product	Identifying Features	Based upon Clinical History of the Following
Straight, Cementless Modular Stem	TMZF® Alloy Plasma Spray PureFix™ HA	Omnifit® HA Secur-Fit™ HA

The Omnifit® HA femoral component has long-term survivorship in a relatively young patient group, with a low mechanical failure rate compared to other fixation methods at similar lengths of follow-up. A total of 166 hips (146 patients) were followed for an interval of 15 to 18 years, with both femoral aseptic revision and mechanical failure rates at approximately 0.6%.⁴ Omnifit® is considered Stryker's gold standard for proximal HA-coated femoral stems. The Rejuvenate® Modular Hip System is an updated version of the Omnifit®, modifying the C-taper trunnion and bulky neck geometry. These features are considered weaknesses of the Omnifit® design.

The Secur-Fit™ system, the historical control for this clinical study, was based on the geometry of the Omnifit® femoral stem. The Secur-Fit™ HA stem retains the Omnifit® geometry, normalized design and PureFix™ HA coating to further enhance initial stem stability and augment proximal load transfer. The Secur-Fit™ HA stem has a highly polished neck, decreasing the potential for polyethylene debris. Each implant maintains the same geometry, regardless of stem size, allowing the stems to more closely match natural anatomy.

In a clinical and radiographic review by Jaffe and Hawkins⁵ of 215 THRs in which a monolithic, normalized, proportionalized, cemented femoral component was implanted, the design was reported to allow for more efficient force transmission between prosthesis, cement and bone and to lessen failure rates at these interfaces. Overall, the study showed an aseptic failure loosening rate of 3.9% at 15 years for the stem. These results were favorable when compared with other first generation and second generation stems at similar follow-up.⁶ Although the Rejuvenate® Modular Hip System is intended for cementless application, the findings by Jaffe and Hawkins⁷ focus on a normalized femoral component. As with the femoral stem studied, the Rejuvenate® Modular Stem includes a normalized pattern on the anterior and posterior aspects of the proximal end of the stem, facilitating load transmission in the proximal region of the femur.

CONFIDENTIAL

The Secur-Fit™ system is the direct predecessor for the Rejuvenate® Modular Hip System. The Rejuvenate® Modular Hip System introduces the concept of modularity, offering the surgeon additional intraoperative flexibility. The mixing and matching of components, as described further in Section 6, Device Description, allows the surgeon to choose the best anatomical fit for the patient. The Rejuvenate® Modular Hip System permits the matching of a proximal femoral neck in different lengths, angles and version, with different sizes of distal stems.

This clinical study is necessary to compare the success of the Rejuvenate® Modular Hip System to the reported success of its monolithic predecessor. The objective of the study is to show that neck modularity has not changed the survivorship of standard primary hip femoral components.

1.2 *Investigational Device*

The Rejuvenate® Modular Hip System is fabricated from TMZF® alloy and features the PureFix™ HA fixation philosophy. The stem is built upon the design features and clinical history of the existing Omnifit® and Secur-Fit™ Stryker femoral stems. The device provides better patient matching by allowing for interchange of the femoral neck angle, femoral neck length, version and femoral head offset. The Rejuvenate® Modular Hip System has a modular neck, allowing for 127°, 132° and 130° femoral neck angles. The 130° modular neck is only available in the 16° version option. Four femoral neck lengths are available, ranging from 30 mm to 42 mm, in 4 mm increments. Possible overall neck lengths range from 26 mm to 46 mm, utilizing V40 +/- 4 mm femoral heads.

The Rejuvenate® Modular Hip System is intended for use in a cementless application. It is designed to address the need for greater accuracy in reproducing offset, leg length and femoral neck version, as well as optimize range of motion (ROM) for primary hip patients. Data in support of these marketing claims will be collected in the Rejuvenate® Modular Hip System Outcomes Study.

CONFIDENTIAL

The Rejuvenate® Modular Hip System is cleared for use as follows:

- FDA 510(k) K071082, original submission for sizes 7, 8, 9 and 10
- FDA 510(k) K081044, line extension for compatibility between the size 9 stem and the 42 mm neck
- FDA 510(k) K092561, for use with up to 46 mm of total neck length

1.3 Preclinical Data

The following bench tests were conducted on the Rejuvenate® Modular Hip System:

Description of the test	Report ID
Mod. ISO-Neck Fatigue	– RD-07-029
ISO 7206-4 Distal Fixation Model	– RD-07-028
Fretting Size 7	– RD-07-054
Fretting Size 10	– RD-07-100
Flexion	– RD-07-101
Revision	– RD-07-056
Pull-off Strength/Disassembly	– RD-07-055

Copies of all test reports are available at Stryker Orthopaedics.

1.4 Clinical Data to Date

A limited number of evaluation instrument sets and implants have been distributed in the United States to date. Anecdotal feedback from the centers has been positive. This study is the first prospective data collection on the Rejuvenate® Modular Hip System.

2 Study Objectives

2.1 Efficacy

2.1.1 Primary

The primary objective of this study will be to evaluate the success rate of cementless primary THR with the Rejuvenate® Modular Hip System, as compared to the Secur-Fit™ HA monolithic femoral hip stem, a historical control. Success will be defined as absence of femoral stem/neck construct revision/removal for any reason at 5 years postoperative. It is expected that the survivorship of the Rejuvenate® Modular Hip

CONFIDENTIAL

System group will be non-inferior to the survivorship reported for Secur-Fit™ HA monolithic femoral hip stem cases enrolled in the Trident® X3® Polyethylene Insert Study.

2.1.2 Secondary

The secondary objectives of this study will be to measure natural preoperative biomechanical measurements for creation of a preoperative plan, and compare to postoperative biomechanical measurements, within the Rejuvenate® Modular Hip System group. It is expected that the postoperative measurements at the 6-week interval will be similar to the preoperative plan.

Additionally, pain, function and health-related QOL between the Rejuvenate® Modular Hip System group and the Secur-Fit™ HA monolithic femoral hip stem group will be compared at postoperative time points. It is expected that the HHS, SF-12 and LEAS outcomes in the study group will be non-inferior to the historical control.

Lastly, radiographic stability and complications between those implanted with the Rejuvenate® Modular Hip System and the Secur-Fit™ HA monolithic femoral stem group will be reviewed. Published complication rates with similar devices as well as complications related to modularity will be reviewed, as applicable.

Clinical Outcomes:

Clinical outcomes will be evaluated via the total HHS, including pain, motion and function, preoperatively, and at the 6-week, 1, 2, 3, 4 and 5-year visits. Additional HHS data will be obtained at the 7-year and 10-year time points at investigational sites that choose to bring their subjects back in for these optional visits.

Patient Outcomes:

The SF-12 is a 12 item patient self-assessment evaluating health and general well being. The LEAS is a tool that has been developed and validated to evaluate the level of patient activity. These tools will be used to assess patient health-related QOL and will be collected preoperatively, at the 6-week, 1, 2, 3, 4 and 5-year visits. Additional patient outcomes data will be obtained at the 7-year and 10-year time points at investigational sites that choose to bring their subjects back in for these optional visits. A questionnaire

CONFIDENTIAL

for patient completion, intended to provide information on patient satisfaction, pain and whether or not there have been any revisions or removals of the study device since the last follow-up visit, is required at the 6, 7, 8, 9 and 10-year visits.

Radiographic Outcomes:

Radiographs will be taken and collected in the AP pelvis, AP femur and lateral views for the preoperative, 6-week, 1, 2, 3, 4 and 5-year intervals. Additional radiographs will be obtained at the 7-year and 10-year time points at investigational sites that choose to bring their subjects back in for these optional visits.

The AP pelvis and AP femur views allow for observations of any conditions involving the sacral wings, iliac bones, ischium, pubis as well as the femoral head and neck. These views additionally display the critical relationship between the femoral neck's longitudinal axis and the femoral shaft's longitudinal axis for identification of displacement in the event of a femoral neck fracture. The lateral view allows for evaluation of the entire hip joint as well as specifically the femoral head, neck and proximal shaft.⁸ Suggested radiographic technique for the views required is included in Appendix A.

Radiographs will be evaluated by an independent reviewer throughout the course of the study. Radiographic analysis of the femoral component will employ seven zones (Zone 1 - Zone 7) in the AP views and seven zones (Zone 8 – Zone 14) in the lateral view; analysis of the acetabular component will employ three zones (Zone 1 – Zone 3) in the AP views.^{9,10} Numerous parameters will be reviewed by zone, including radiolucency, hypertrophy, and condensation. Radiolucency in at least 50% of a zone and measuring at least 1 mm in width is defined as radiolucency present.

Subsidence, migration and fixation will also be assessed. Subsidence is defined as settling of the prosthetic component in bone, and is related to the distance between fixed bony landmarks and the prosthesis.

CONFIDENTIAL

Biomechanical Measurements:

Preoperatively, study radiographs will be taken by each investigator. From these radiographs, each investigator will determine natural measurements and provide a detailed picture of each patient's level of deformity, as follows.

- Leg length discrepancy (centimeters)
 - Measurement of leg length discrepancy should be determined from the AP pelvis radiograph by drawing lines across both pelvic teardrops to meet both femurs. These lines are to be used as the main reference lines for measuring the distance to the top of each lesser trochanter.¹¹ The difference between these distances is the value of leg length discrepancy.
- Natural femoral offset (millimeters)
 - Femoral offset should be determined by measuring the perpendicular distance from the center of the femoral head to the axis along the length of the femur.¹²
- Natural femoral neck angle (degrees)
 - Femoral neck angle is the angle between the long axes of the femoral neck and femoral shaft.¹³
- Qualitative assessment of natural femoral version (Retroverted, Neutral, Anteverted)
 - Proximal femoral version reflects the relationship of the axis of the femoral neck to the transcondylar axis of the distal femur.¹⁴ Qualitative determination of whether natural femoral version is retroverted, anteverted or in a state of neutral version should be made from the lateral radiograph.

The investigator at each center will create a preoperative biomechanical measurement plan for each case from templating, reflecting desired postoperative measurements and the component sizes, angles and offsets that will be used to achieve these measurements. All component sizes should be corrected for magnification (if any) prior to data collection on the study Case Report Form (CRF). This may be accomplished by utilizing an external radiographic marker of known dimension prior to taking the preoperative radiograph.¹⁵

CONFIDENTIAL

Preoperative Distance from Planned Center of Rotation

- Vertical distance from the anatomic hip center to the planned center of rotation of the hip (millimeters)
- Horizontal distance from the anatomic hip center to the planned center of rotation of the hip (millimeters)

Components to be Used

- Acetabular cup size
- Femoral neck angle [127°, 132°, 130° (16° version option only)]
- Femoral neck length (millimeters)
- Femoral head size
- Femoral head offset
- Femoral stem size*
- Femoral version (0°, ±8°, ±16°)

*The Rejuvenate® Modular Stem will be available in sizes 7, 8, 9, 10, 11 and 12. The Rejuvenate® Monolithic Stem will be available in sizes 4, 5 and 6; however, **the Rejuvenate® Monolithic Stem may not be used according to this protocol.** Patients requiring a femoral stem in size 4, 5 or 6 should not be enrolled into the study. Investigators should template the femoral stem size to be used prior to completing the Inclusion/Exclusion CRF for enrollment into the study.

Additional Planned Measurements

- Amount of leg length to be restored (centimeters)
 - Measurement of leg length discrepancy should be determined from the AP pelvis radiograph by drawing lines across both pelvic teardrops to meet both femurs. These lines are to be used as the main reference lines for then measuring the distance to the top of each lesser trochanters.¹⁶ The difference between these distances is the value of leg length discrepancy. From this value, the investigator will determine the amount of leg length he/she plans to restore.
- Femoral offset to be achieved (millimeters)
- Qualitative assessment of postoperative planned femoral version (Retroverted, Neutral, Anteverted)

A postoperative check of biomechanical measurements will be performed by the investigator at each site from the 6-week radiographs to confirm the degree to which the

CONFIDENTIAL

preoperative plan was achieved. If an AE for instability exists, the postoperative check will be taken again at applicable postoperative intervals to confirm whether or not changes have occurred.

Postoperative Distance from Planned Center of Rotation

- Vertical distance from the postoperative hip center to the planned preoperative center of rotation of the hip (millimeters)
- Horizontal distance from the postoperative hip center to the planned preoperative center of rotation of the hip (millimeters)

Additional Postoperative Measurements

- Leg length discrepancy (centimeters)
- Final femoral offset (millimeters)
- Final femoral neck angle used [127°, 132°, 130° (16° version option only)]
- Qualitative assessment of replaced femoral version (Retroverted, Neutral, Anteverted)

These postoperative values will be compared to the preoperative plan to evaluate the degree of patient matching achieved with the Rejuvenate® Modular Hip System.

Component sizes used intraoperatively will be automatically determined from catalog numbers provided on the Surgical Details CRF.

Biomechanical measurements are outlined in Appendix B.

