9.1.2 Secondary Efficacy Parameters

The secondary efficacy parameters include:

- Biomechanical measurement change from preoperative plan at 6-week visit
- HHS at each visit
- SF-12 scores at each visit
- LEAS at each visit

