9.1.5 Secondary Efficacy Analysis

A two-sided 0.05 alpha level will be used.

For comparison of biomechanical measurements between a preoperative plan and postoperative measurements within the Rejuvenate[®] Modular Hip System group, a t-test or Wilcoxon test will be used.

Independent group t-tests will compare HHS, SF-12 and LEAS at each time point between the Rejuvenate[®] Modular Hip System and Secur-Fit[™] HA monolithic femoral stem groups. In addition, a paired t-test will compare the results preoperatively with each postoperative evaluation within the Rejuvenate[®] Modular Hip System group.

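### Section 2.1.2 expects non-inferior scores and biomechanics close to plan, but section 9.1.5 offers only unadjusted difference tests with no margin or tolerance, so a non-significant result would support neither

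*Combined protocol and SAP*

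**What the plan says.** **Scores.** Section 2.1.2 sets the expectation: "It is expected that the HHS, SF-12 and LEAS outcomes in the study group will be non-inferior to the historical control". The matching analysis in section 9.1.5 reads "Independent group t-tests will compare HHS, SF-12 and LEAS at each time point between the" two groups, under the rule "A two-sided 0.05 alpha level will be used". The synopsis names the same tests.

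**Biomechanics.** Section 2.1.2 adds: "It is expected that the postoperative measurements at the 6-week interval will be similar to the preoperative plan". Section 9.1.2 defines the parameter as "Biomechanical measurement change from preoperative plan at 6-week visit". The synopsis gives the analysis: "A t-test or Wilcoxon test will be used to compare the postoperative biomechanical measurements to a preoperative plan". Section 9.1.5 repeats it.

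**What exists elsewhere.** Only the primary revision endpoint has a margin and a confidence-bound rule (synopsis and sections 9.1.3, 9.1.4 and 9.4.2). No secondary endpoint has a margin, a tolerance, a covariate or a sample-size calculation.

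**Use of the data.** Section 1.2 says the study will supply data for marketing claims about accuracy in reproducing offset, leg length and version.

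**The concern.** Non-inferiority and similarity are statements about how large a difference could still be. A two-sided test of no difference does not answer that: failing to reject is compatible with a material deficit, and the smaller or noisier the data, the easier it is to fail to reject.

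For the scores, the comparison is also non-randomised, against cases from another study. Differences in preoperative status could create or hide a difference, and the planned t-tests do not adjust for the preoperative score, although this study collects it on all three scales.

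For the biomechanics, accuracy means the size of the error in each hip. A test of the mean or median signed difference lets overshoot and undershoot cancel. For several of the listed items, the values before and after surgery are not the same quantity, so the stated test has no clear meaning.

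**Working it through.** **Inputs from the documents.** Two-sided alpha 0.05 (section 9.1.5). 240 cases per group, 20% drop-out and 147 evaluable cases per group for the primary endpoint (section 9.4.2). 240 × 0.8 = 192 per group is taken as the main case. The plan states no secondary-endpoint figure to reproduce.

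**Assumptions.** HHS SD 15 (range 10 to 20) and a true deficit of 3 points; SD of the per-hip offset error 6 mm (range 4 to 8) and a 5 mm tolerance. None of these comes from the documents.

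**1. Scores: what a non-significant t-test leaves open.** The largest observed deficit that stays non-significant is t(0.975, 2n−2) × SD × √(2/n). The 95% interval then extends to twice that deficit.

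| n per group | SD | Largest non-significant deficit | Interval reaches |
|---|---|---|---|
| 192 | 10 | 2.01 | 4.01 |
| 192 | 15 | 1.966 × 15 × √(2/192) = 3.01 | 6.02 |
| 192 | 20 | 4.01 | 8.03 |
| 147 | 15 | 3.44 | 6.89 |
| 240 | 15 | 2.69 | 5.38 |

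**2. Scores: chance of missing a real deficit.** With a true deficit of 3 points and n = 192, the noncentral t distribution with noncentrality (3/SD) × √(n/2) gives a non-significant result with probability 0.166, 0.502 and 0.689 for SD 10, 15 and 20. In SD units, a 0.20 SD deficit is missed 50% of the time at 192 per group and 41% at 240.

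**3. Scores: number of tests.** Three instruments at six postoperative visits make 18 tests. If they were independent, the chance of at least one false difference would be 1 − 0.95^18 = 0.60. They are correlated, so this is a rough upper figure.

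**4. Biomechanics: are plan and follow-up comparable?** Section 2.1.2 lists six postoperative items:

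| Item | Before surgery | At 6 weeks | Same continuous quantity? |
|---|---|---|---|
| Vertical centre of rotation | anatomic to planned | achieved to planned | No: the later value is itself the error |
| Horizontal centre of rotation | anatomic to planned | achieved to planned | No: same reason |
| Leg length | amount to restore | remaining discrepancy | No |
| Femoral offset | mm to achieve | mm achieved | Yes |
| Neck angle | one of three values | one of three values | Discrete |
| Version | three categories | three categories | Categorical |

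Only offset suits the stated test directly. Section 9.1.2 speaks of change from plan, but nothing says how each pair is formed; section 9.1.5 uses the word paired only for the scores. Leg length is in centimetres in section 2.1.2 and Appendix B but in millimetres in sections 7.1 and 7.3.

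**5. Offset: what the mean test hides.** With zero mean error and normal errors, the limits of agreement are ±1.96 × SD and the share of hips within 5 mm is 2Φ(5/SD) − 1.

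| SD (mm) | Limits of agreement (mm) | Within 5 mm |
|---|---|---|
| 4 | ±7.8 | 78.9% |
| 6 | ±11.8 | 59.5% |
| 8 | ±15.7 | 46.8% |

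In every row the true mean difference is zero, so the test is expected to show no difference. Conversely, at SD 6 the smallest significant mean shift is t × SD/√n = 0.85 mm (n = 192) or 0.76 mm (n = 240).

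**The case against.** The strongest reply is that section 2.1.2 states an expectation, not a hypothesis. The synopsis objective and section 9.1.5 speak only of comparing, the only formal hypothesis is the primary one, and nothing says a non-significant secondary test will be read as non-inferiority or similarity. That is fair on wording. But an expectation written into the objectives, with no analysis able to confirm or refute it, invites exactly that reading.

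Second, a 95% interval follows directly from the planned t-test, and section 9.4.1 promises descriptive tables that might show scatter. Both are true, but an interval cannot be judged without a margin fixed in advance. The listed summaries are introduced for preoperative and demographic data, and no error per hip is defined.

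Third, the achieved-to-planned distance already captures the centre-of-rotation error for each hip, and leg length can be reconciled by subtraction. Both are possible, but the plan does not say so, and the stated test would compare unlike quantities.

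Fourth, the SDs, the 3-point deficit and the 5 mm tolerance are assumed, and SF-12 and LEAS have no figures. This stands: the numbers illustrate the problem; they do not measure it in this study. The cancellation argument is likewise shown only for offset.

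Finally, the unit mismatch is editorial, and the forms as extracted may have lost a numeric leg-length box. Neither carries the main point.

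**Conclusion.** The concern holds. The plan sets two secondary expectations that its analyses cannot establish, and for centre of rotation and leg length the stated test does not compare like with like. The absence of a margin, tolerance and baseline adjustment is plain from the text and rests on no assumption.

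The size does rest on assumptions. At HHS SD 15 and 192 per group, a non-significant result can coexist with an interval reaching a 6-point deficit, and a true 3-point deficit goes undetected half the time (17% to 69% over SD 10 to 20). For offset, roughly half to four-fifths of hips would be within 5 mm over SD 4 to 8 mm, with the same expected test result throughout.

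The plan should be changed on this point, but the matter is confined to secondary endpoints. The primary revision comparison is unaffected.

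**What to change.** **Scores.** Replace the t-tests with ANCOVA adjusted for the preoperative score on the same scale, plus age, sex and BMI where the control data hold them. Name one key time point, such as 5 years. Report the adjusted difference with its 95% interval, and claim non-inferiority only if the lower bound lies above a margin stated in advance for that scale. If no margin can be justified, replace the non-inferiority wording in section 2.1.2 with descriptive wording.

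**Biomechanics.** Define the error for each hip:
- offset: achieved minus planned;
- centre of rotation: the postoperative distance to the planned centre is itself the error;
- leg length: planned residual discrepancy = preoperative discrepancy minus planned restoration, and the error is the achieved discrepancy minus that value.

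Report mean absolute error, the percentage of hips within a stated tolerance, limits of agreement where values are signed, and percentage agreement for version and neck angle. Use one leg-length unit throughout.

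**Cost.** SAP wording and programming, with no extra patients or visits. The sponsor must commit to margins and tolerances before looking at the data. It must also confirm that the control study holds patient-level preoperative scores and covariates, and that the CRF records a numeric radiographic leg-length discrepancy; the forms as extracted show only yes/no and the longer side. If either is missing, that item should be described only.
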